## **8 PROJECT MANAGEMENT**

### **8.1 Project steering committee**

There will be a project steering committee led by the principal investigator and project coordinator to follow up all the project phases and to overcome possible problems. [name], [name], [name], [name] are responsible for study design, quality assurance and report writing. Local investigators and coordinators of data collection: [name].

### **8.2 Dissemination of results and publication policy**

The results of this study will be published in a peer-reviewed medical journal. We have no restrictions in publication of outcomes of this study.

### **8.3 Problems anticipated**

Although this study is an interventional study, the treatment that is performed in the study is the usual neonatal treatment. Patients are constantly monitored throughout the study to minimize risk.

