## 1. PROJECT SUMMARY

**Rationale:** In order to help premature babies, especially premature babies weighing around 1000 g, reliable equipment to provide thermoneutral environment to minimize energy consumption of the newborn is prerequisite. However, newborn devices in developed countries are very expensive and have a complex structure mostly operated with electric power supply, and high expertise is required to use them. Low cost, simple and sustainable incubator is required in resource limited settings where electric power supply is frequently unreliable. Development of a low-cost, simple and effective incubator has been undertaken by a Japanese perinatal medical device manufacture, ATOM Co,Ltd., and prototypes of the equipment has been now available. The study aims to examine the effectiveness of the incubator in resource limited settings in Special Care Baby's Care Unit (SCBU) in Ola During Children's Hospital.

**Objective:** i .verify the effectiveness in the heat retention of a newly developed incubator for premature babies.

**Hypothesis:** i .Newly developed incubator keeps premature newborn temperature constant.

**Study design:** This is an intervention study at Ola During Children's Hospital

**Study population:** Parturients admitted to Ola During Children's Hospital in Freetown, Sierra Leone.

**Sample size:** During a week period all patients meeting the inclusion and exclusion criteria will be recruited. Based on current rates of admissions in the mentioned services, we expect to recruit at least 6 patients during two weeks data collection period.

**Methods:** Research is conducted on newborns who meet the criteria and are admitted to Ola During Children's Hospital. A patient is accommodated in the newly developed incubator.

All research will be conducted jointly by the Japanese NGO members (a neonatologist and a nurse) and staff at Ola During Children's Hospital. The Japanese neonatologist will always be stationed at the neonatal center during the study period. Local nurses will measure various parameters of hospitalized newborns.

**Main study parameters/primary endpoints:** i . (incubator) Measure body surface temperature and central temperature of newborns in incubator.

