**Nature and extent of the burden and risks associated with participation, benefit and group relatedness:** In this study, we are targeting premature babies that have previously been difficult to be saved at Ola During Children's Hospital which may reduce neonatal mortality. Patients are constantly monitored throughout the study to minimize risk. The use of the incubator may result in insufficient heat retention for the patient even though laboratory tests results showed effectiveness of its capability to keep the patient above 37 degree for 3 hours. In order to avoid this problem, a Japanese neonatologist will monitor the patient for 24 hours per day throughout the study period.

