## **2 INSTITUTIONS INVOLVED IN THE PROJECT**

### **2.1 Ola During Children's Hospital**

Ola During Children's Hospital is a tertiary children's hospital in Freetown, the capital city of the country. It has 250 beds and accommodates approximately 1,000 admissions and 3,000 outpatient consultations per month (personal conversation). Special Baby's Care Unit is a ward specifically dedicated to newborn infants in and out of the hospital, where more than 60% of the total deaths of the hospital occur. Three pediatrician and several other junior doctors are treating the patients and one medical doctor is assigned to SCBU. Currently 8 bubble Continuous Positive Airway Pressure devices, donated by UNICEF, are operational. Two open infant warmers are operational.

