#### 6.1.2 Procedure

1. Weigh neonate if weight is > 800 < 2000, and neonate has stable breathing document initial assessment and obtain informed consent from parent
2. Fill the plastic bottle with boiled water and put it in the incubator. We boil clean water by our electric kettle.
3. Assemble incubator
4. Place the bottle in the foil wrap and secure in designated position in the incubator at each end

5. Use hygrometer to confirm that internal incubator temperature is greater than 32 degrees Celsius and less than 37 degrees Celsius.
6. Place neonate inside incubator ensure they are stable.
7. Use data collection sheet to assess each parameter every **15 minutes for the 1st hour** if the baby is stable (maintain the baby's temperature and not change the breathing condition) , we measure the parameter **every 30 minutes**. If the temperature in the incubator exceeds 37° ,open the incubator for 5 minutes and measure the temperature again.
8. Newborn in the incubator always wear a pulse oximeter.
9. Measure without opening the incubator
10. We follow the ODCH doctor's instructions for the interval and methods of feeding.
11. Local nurses observes the newborn in an incubator for 24 hours and then return the newborns to cot.
12. Call a local medical doctor if the newborn has the following problems during our monitoring.: 1) the newborn's respiratory condition deteriorates, 2) the newborn has problem with their feeding patterns and vital signs.
13. Change the hot water to keep the newborn's temperature between 36.5°C and 37.2°C.
14. Wipe once a day with clean water. When replacing the newborn, disassemble the incubator and disinfect with alcohol.
15. measure the water temperature.

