## **7.2 Statistical analysis**

This study only records biological parameters and temperature. If we get past neonatal mortality data at Ola During Children's Hospital , we compare the survival rates using Kaplan-Meier method.

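### Section 8.3 calls the study treatment usual, but every infant gets a prototype incubator and a stationed visiting neonatologist, so the past-data survival comparison in Section 7.2 cannot show an incubator effect

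*Protocol*

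**What the plan says.** Section 8.3 (Problems anticipated) concedes that the study is interventional, but then says that "the treatment that is performed in the study is the usual neonatal treatment".

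The Project Summary describes something else. Of the device it says that "prototypes of the equipment has been now available", and of each participant that "A patient is accommodated in the newly developed incubator". On staffing it says: "The Japanese neonatologist will always be stationed at the neonatal center during the study period". Its paragraph on burden and risk adds that "a Japanese neonatologist will monitor the patient for 24 hours per day throughout the study period". Section 2.1 gives the background: "one medical doctor is assigned to SCBU", and the warming equipment listed as working is two open infant warmers.

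Section 7.2 (Statistical analysis) says that, if past neonatal mortality data from the hospital are obtained, "we compare the survival rates using Kaplan-Meier method". It does not say which past infants would be used or how a difference would be interpreted. Section 6.1.4 rules out randomisation, and Section 6.2 marks study groups as not applicable.

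**The concern.** A reader told that treatment was usual will take the incubator as the one thing separating study infants from past infants. On the protocol's own account at least two things change together: the warming device and the presence of a neonatologist. Section 5.1 also selects the study infants, and Section 7.2 does not ask for the same selection in the past data.

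What is at stake is the survival statement. Section 3.3 hopes the equipment will lead to a better chance of survival, and Section 9.3 mentions lower neonatal mortality alongside the new devices. A favourable Kaplan-Meier curve would be read in that light, although the design cannot say which component produced it.

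**Working it through.** The protocol has no figure to reproduce here. The expected recruitment of at least 6 infants rests on admission rates that are not quantified. The check sets the passages side by side and then asks what the comparison can identify.

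**1. Study care against the unit's described resources**

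| Element | Study infants | Unit as described (Section 2.1) | Shown to differ? |
|---|---|---|---|
| Warming | Prototype incubator (Project Summary) | Two open warmers | Yes |
| Physician cover | Visiting neonatologist always stationed, monitoring 24 hours a day (Project Summary) | One assigned doctor | Yes |
| Nurse observation | Local nurses, 24 hours (Section 6.1.2, step 11) | Not described | No |
| Pulse oximetry | Worn throughout (Section 6.1.2, step 8) | Not described | No |
| Feeding | As hospital doctors instruct (step 10) | Not described | Appears unchanged |

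The first two rows are enough to contradict Section 8.3.

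**2. What the survival comparison estimates**

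All study infants have both the device and the added care. No past infant is described as having either. So

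observed difference = device effect + care effect + selection effect + any change over time.

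This is one quantity with several unknowns. No analysis of these data can split it.

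**3. Care effect (survival rates assumed, since the protocol gives none)**

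With a device effect of zero:

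- 0.70 to 0.80 from added care alone: apparent gain 0.10; ratio of deaths 0.20/0.30 = 0.67.
- 0.60 to 0.75: apparent gain 0.15; ratio 0.25/0.40 = 0.62.
- 0.80 to 0.90: apparent gain 0.10; ratio 0.10/0.20 = 0.50.

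**4. Selection effect**

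Section 5.1.2 excludes breathing disorder, sepsis, fatal congenital disease and weights outside 800 to 2000 g. Let f be the fraction of past infants who would have been eligible, with survival s_e in those infants and s_i in the rest. Unrestricted past survival is f·s_e + (1 − f)·s_i. With no effect of device or care, the apparent difference is

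s_e − [f·s_e + (1 − f)·s_i] = (1 − f)(s_e − s_i).

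This is zero only if all past infants were eligible or both groups survive equally. Leaving out very sick or very small infants pushes it up, and leaving out those above 2000 g probably pushes it down. The protocol does not allow its net sign to be determined.

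**5. Exposure against outcome**

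The infant returns to a cot after 24 hours (Section 6.1.2, step 11), while outcome is recorded at discharge (Study period section). Much of the follow-up may lie outside the incubator, which weakens attribution further.

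**6. Chance at n = 6**

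If survival is unchanged at p, the probability that all 6 survive is p^6: 0.016 at p = 0.5, 0.047 at 0.6, 0.118 at 0.7, 0.262 at 0.8 and 0.531 at 0.9. The values of p are assumptions. If all 6 survive, the exact 95% lower limit for survival is 0.025^(1/6) = 0.54. A perfect result would thus be weak evidence even without confounding.

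**The case against.** The strongest reply is that the stakes are low. Survival is not an objective, hypothesis or listed endpoint. The comparison happens only if past data are found, and it would rest on about six infants. The heat-retention question is unaffected. All of this stands, and it limits the point's weight. But the protocol does plan the comparison and sets no limit on its reading.

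A second reply is that usual treatment may mean the medical care around the device: feeding follows hospital doctors, and a local doctor is called for deterioration. That is a fair reading of the intent, but the sentence does not say so, and it does not cover the stationed neonatologist.

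A third is that the bias arises in Section 7.2, so rewording Section 8.3 alone would not remove it. That is correct, and both sections need the edit.

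The documents do not support four stronger readings that a reader might infer:

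- That Section 7.2 credits any gain to the incubator. It has no attribution rule; Sections 3.3 and 9.3 only express hope.
- That the departure from usual care is concealed from the ethics committee. The device, the neonatologist and the monitoring are all stated elsewhere in the same protocol.
- That nurse observation and oximetry exceed routine care. Routine practice is not described, so this is unknown.
- That each infant has 50 rounds of readings in 24 hours (4 + 23 × 2). The data sheet in Section 6.1.1 stops at 360 minutes, which is 4 + 10 = 14 rounds after placement. Step 11 requires 24-hour observation but does not say that readings continue throughout.

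**Conclusion.** The point holds in a limited form. Section 8.3 is wrong as written, because the device and the neonatologist's presence both depart from the resources described in Section 2.1. The survival comparison in Section 7.2, if made, would contrast study-period care in selected infants with past care in infants whose selection is unspecified. It could not isolate the incubator, and a difference could be wrongly credited to it.

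The bias cannot be sized from the protocol. The 10 to 15 points above are illustrations under assumed survival rates, and the net direction of the selection effect is unknown. The conclusion rests on the past infants not having had the prototype or the visiting neonatologist, which the protocol implies but does not state. The correction is worth making because it changes what the trial may conclude about survival. It does not affect the temperature results.

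**What to change.** In Section 8.3, replace the sentence on usual treatment. Say that infants are warmed in an investigational prototype incubator, with added neonatologist presence and study monitoring, and that other care is as directed by hospital doctors. The sponsor should confirm the last part, since the protocol states it explicitly only for feeding and for calls on deterioration.

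In Section 7.2, add that any comparison with past data:

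- is descriptive;
- is limited to past infants meeting the Section 5.1 criteria (800 to 2000 g; no breathing disorder, sepsis or fatal congenital disease) as far as the records allow;
- is reported as study-period care versus past care;
- is not attributed to the incubator.

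The cost is a few sentences. No clinical procedure changes and no data are added for study infants. The downside is a less favourable survival claim and possibly fewer usable past records.

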### **8.4 Timeline of project**

Ethical Clearance: November-December 2019

Training of operators: Jan 2020

Data Collection and Data entry: Feb 2020

Data analysis: Mar-Apr 2020

Preliminary results: May 2020

Final report: July 2020

### **8.5 Amendments**

Amendments are changes made to the research protocol after a favorable opinion by the accredited ethical committee (EC) has been given. All amendments will be notified to the EC that gave a favorable opinion. Non-substantial amendments (typing errors and administrative changes) will not be notified to the accredited EC and the competent authority, but will be recorded and filed by the sponsor.

### **8.6 Temporary halt and (prematurely) end of study report**

In the unlikely event of a temporary halt or early stopping of the study, the investigator/sponsor will notify the accredited EC of the end of the study within a period of 8 weeks. The end of the study is defined as the last patient included. The investigators will notify the EC immediately of a temporary halt of the study, including the reason of such an action. In case the study is ended prematurely, the investigators will notify the accredited EC within 15 days, including the reasons for the premature termination. Within one year after the end of the study, the investigators will submit a final study report with the results of the study, including any publications/abstracts of the study, to the accredited EC.

## **9 ETHICS AND INFORMED CONSENT**

### **9.1 Regulation statement**

This study will be conducted according to the principles of the Declaration of Helsinki (revision Fortaleza, Brazil, October 2013). Approval to carry out this study will be sought from the relevant Review Board of Sierra Leone Ethics and Scientific Review Committee.

### **9.2 Informed consent process**

An investigator or designee will describe the protocol to potential subjects face-to-face. The key information about the purpose of the study, the procedures and experimental aspects of the study, risks and discomforts, any expected benefits to the subject, and alternative treatment will be presented first to the subject.

Subjects will also receive an explanation that the trial involves research, and a detailed summary of the proposed study procedures and study interventions/products. This will include aspects of the trial that are experimental, the expected duration of the subject's participation in the trial, alternative procedures that may be available and the important potential benefits and risks of these available alternative procedures.

### **9.3 Benefits and risks assessment**

In this study, we are targeting premature babies that have previously been difficult to help at Ola During Children's Hospital, which may reduce neonatal mortality. New neonatal devices are made over conventional neonatal devices. In addition, the safety of these devices has been confirmed by experiments, and there is almost no risk.

## 10 BUDGET AND OTHER SUPPORT FOR THE PROJECT

Doctors and nurse are will be giving a little token as a research fee after the research. However, the newborn device will be provided by Atom Co., Ltd.

## 12.APPENDIX

### Neonatal Management Package - Instructions for use

[figure not shown]
[figure not shown]
#### 1. Purpose

##### I. Warmer

This product is intended to warm the inside of the unit and prevent a neonate from developing hypothermia.

#### 2. Name of each component

##### I. Warmer

Number	Name	Function
①	Hood	To secure internal air isolation and gain visibility of the inside.
②	Mattress	To lay a neonate down.
③	Hot water bottles	To warm up the inside of the unit with hot water in the bottles.

### 3. Performance test results

The results of the performance tests conducted for the warmer are as follows.

- Heat insulation capacity

Pour 2 liters of 38 Degree Celsius water, the average normal body temperature of neonates, into an aluminum can and place it inside of the warmer as a testing model of a neonate. Measure the core temperature of the testing model and count the time until it becomes lowered to 35 Degree Celsius, which is the temperature causing hypothermia, with an ambient temperature and humidity outside of the warmer set at 25 Degree Celsius and 50 % RH respectively. The measurement result is as shown below Figure 1.

[figure not shown]

Figure 1 – The test result obtained from the evaluation on the heat insulation capacity performed by the testing model of a neonate

From Figure 1, it was proven that this product was able to keep warming the testing model of a neonate for a little over 150 minutes with the temperature inside of the warmer being kept at 32 ~30 Degree Celsius during that period.

- Comparison between the core and back temperatures of the testing model  
Due to the nature of this product which supplies heat from under the mattress, the risk associated with the use is a potential scald on the surface skin of the back of a neonate, which the heat source has the closest contact with. To confirm safety, the back and core temperatures of the testing model of a neonate placed inside of the warmer were measured for comparison with an ambient temperature and humidity outside of the warmer set at 25 Degree Celsius and 50 % RH respectively. The measurement result is as shown below Figure 2.

[figure not shown]

Figure 2 – The test result obtained from the comparison made between the core and back temperatures of the testing model of a neonate

From Figure 2, it was proven that since the temperature applied to the back did not exceed the core temperature, there should be no risk of scald with this product.

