- III. It does not require power supply as it generates heat and humid air from hot water tank stored beneath the bed.
- IV. The cost of the incubator is about 1/100 of the incubator used in developed countries.

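### The protocol names a scald as the hazard of the device and declares it ruled out from a model test, but no trial step checks the skin nearest the hot-water bottles

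*Protocol*

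**What the plan says.** The appendix to the protocol (item 3, Performance test results) states that, because heat comes from below the mattress, "the risk associated with the use is a potential scald on the surface skin of the back of a neonate". It reports one comparison of back and core temperature on a testing model, at 25 °C and 50 % relative humidity outside the unit. The back was no warmer than the core, and the appendix takes this as proof that "there should be no risk of scald with this product". Section 6.3.2 adds that the surface of a doll did not reach burning temperatures, without giving any. Section 9.3 says experiments have confirmed safety and puts the remaining risk near zero. The risk paragraph in section 1 discusses only insufficient warmth.

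For the trial itself, section 6.1.2 step 2 reads "Fill the plastic bottle with boiled water and put it in the incubator". Step 13 has the water changed to hold the infant at 36.5 to 37.2 °C, and step 11 reads "Local nurses observes the newborn in an incubator for 24 hours and then return the newborns to cot". Step 4 secures the foil-wrapped bottles at the two ends of the unit. Section 3.2 says instead that "it generates heat and humid air from hot water tank stored beneath the bed".

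The data sheet in section 6.1.1 has a single infant temperature, taken at the armpit. The primary endpoint in section 1 names both a body surface and a central temperature.

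**The concern.** A hazard that the plan itself identifies would normally lead to a bedside check and a rule for acting on what is found. Here the bench result is used to close the question, and the trial procedure contains neither. The one temperature limit that triggers an action on the device, 37 °C in step 7, applies to the air in the unit. Readings are to be taken without opening it (step 9). An injury to skin lying against a warm surface could therefore go unseen until the infant is next handled.

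Two things are at stake. One is the safety of preterm infants close to freshly boiled water in a prototype device. The other is the accuracy of the risk assessment in the protocol that goes to the ethics committee.

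**Working it through.** The plan gives no figure for scald risk, so there is none to reproduce. The check compares what was tested, what the trial does and what the trial monitors.

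**What the bench work covers**
- Subject: a testing model (appendix) and a doll (section 6.3.2).
- Ambient condition: 25 °C and 50 % relative humidity in the appendix; none stated for the doll.
- Model size: the retention test in the same appendix begins "Pour 2 liters of 38 Degree Celsius water". At 1 kg per litre that is 2.0 kg. If the back test used the same model (an assumption), it matches the heaviest eligible infant (2.0 / 2.0 = 1) and has 2.0 / 0.8 = 2.5 times the mass of the lightest.
- Conclusion: no limit on water temperature, infant weight or bottle position.

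**What the trial does**
- Infants of 800 to 2000 g, boiled water, refills as needed, 24 hours (sections 5.1.2 and 6.1.2, steps 2, 11 and 13).
- Bottles at the two ends (step 4), against a source beneath the bed (section 3.2) or under the mattress (appendix). If step 4 governs, the nearest skin may be the head or feet, and the geometry may not be the one in which the back was tested.

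**What the trial monitors**
- Steps in section 6.1.2 that measure or inspect skin near the heat: 0 of 15.
- Reasons to call the doctor (step 12): breathing, feeding and vital signs. No skin sign.
- Water temperature: on the sheet and in step 15, with no action limit.
- Infant temperatures on the sheet: 1 of its 11 columns, against 2 named in section 1. If the armpit stands for the central reading, the surface reading is missing; if it stands for the surface reading, the central one is.

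**Number of checks the fix would need**
- Assume one fill lasts from 150 minutes (appendix) to 180 minutes (section 6.3.2).
- Fills in 24 hours: 1440 / 180 = 8, to 1440 / 150 = 9.6, so 10.
- Changes after the first fill: 8 − 1 = 7, to 10 − 1 = 9 per infant.
- For six infants: 7 × 6 = 42, to 9 × 6 = 54.

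**What six infants could show**
- With no scald in six inspected infants, the one-sided 95% upper bound on the risk is 1 − 0.05^(1/6) = 39.3%. Inspection would protect the infants in the trial; it would not establish that the device is free of scald risk.

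**The case against.** The plan is not without protection. There is an insulating mattress (section 6.3.2), foil around the bottles (step 4), a transparent hood (appendix, item 2), continuous observation by nurses and a neonatologist, adverse event recording, and withdrawal for urgent medical reasons (section 6.4.1). The appendix also says there should be no risk, which is slightly short of a flat denial. All of this stands and makes a serious injury less likely. But none of it directs anyone to the skin nearest the bottles, and a hood does not show the back of an infant lying on it.

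Several stronger readings are tempting, and the documents do not support them:

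- A reader might infer that the back test was run without a recorded water or chamber temperature. Its result is in Figure 2, which is not shown and may give both.
- A reader might set the retention test, "the temperature inside of the warmer being kept at 32 ~30 Degree Celsius during that period", against step 5, "Use hygrometer to confirm that internal incubator temperature is greater than 32 degrees Celsius and less than 37 degrees Celsius", and conclude that the device was tested cooler than it will be used. The ranges do not overlap, but the first belongs to a different test, and both are air temperatures that say nothing direct about contact heat.
- A reader might divide 24 hours by the bench duration and call exposure many times longer than tested. Water is hottest just after each fill, so total time is a poor measure of scald exposure. The printed length of the data sheet does not bear on scald either.
- A reader might infer that parents are told there is practically no risk. The consent pages are not available, and section 9.2 says risks will be explained.

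**Conclusion.** The point holds as a gap between a named hazard and the trial procedure. The no-scald wording is too strong for a model test at one ambient temperature. No step checks the skin nearest the bottles, and neither a skin sign nor the water temperature triggers any action. Bottle position is described inconsistently, so it is unclear which skin is nearest. One of the two infant temperatures named as the main parameter is not collected.

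The documents do not show that the device scalds. They give no back, mattress or bottle-water temperature in the text, so the size of the risk cannot be computed in either direction. This is a low-cost safety improvement to make before enrolment, and it does not make the temperature results unusable. The one comparison that rests on an assumption is the 2.5-fold mass difference, which requires that both appendix tests used the same model.

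**What to change.** 1. In section 6.1.2, steps 12 and 13: at each hot-water change, inspect and record the skin nearest the bottles. That means the back and, if the bottles sit at the ends, also the head and feet. Make redness or a burn a reason to remove the bottles, rewarm the infant by another means and call the doctor. State one bottle position throughout, and exempt this inspection from step 9.
2. Limit the safety wording in the appendix and in sections 6.3.2 and 9.3 to the model and conditions tested. List scald as a risk in section 9.3 and in the risk paragraph of section 1.
3. Add a body surface temperature column to the sheet in section 6.1.1 so that it agrees with section 1, preferably at the skin site nearest the heat. Any action limit should be an absolute skin temperature set before enrolment. A rule based on the back being warmer than the armpit should be avoided: a back at 36.6 °C with an armpit at 36.5 °C would remove the only heat source from an infant at the lower edge of the target range.

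Cost: about 7 to 9 inspections per infant (42 to 54 for six) on the assumed refill interval, done by staff already present when the water is changed; one extra column; and a few wording changes. The downsides are a brief heat loss at each check and, if a probe is used, possible irritation of preterm skin.
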